Lenalidomide 10 mg po daily, with escalation up to 25 mg on days 2-22 of 28 day cycle for patients with small lymphocytic lymphoma for cycles 1-6. Lenalidomide 10mg po daily for days 2-22 for cycles 7-12. Rituximab 375mg/m2 IV x1 on day 1,8,15 and 22 of cycle 1 and on day 1 of every subsequent cycle. Total 12 cycles.

Confidential

2. Schedule of Study Assessments

Procedure 8*	Screening < 30days from Baseline (First day study drug		Cycle 1	_		All Cycles	After Cycles 3, 6, 9,12	Discontinuation From Study Drug	Follow-Up Phase
	administration)	Day	Day	Day	Day	Day	Day		Every 3 ⁶
		-	ω	15	22	-	-		months
Record prior medications, treatments	×								
Record prior anti-cancer therapies	×								
HIV and Hepatitis B/C screening	×								
Physical examination, vital signs, weight	×					×		×	
ECOG performance status	×					×		×	
CT of the chest & abdomen / pelvis, neck, PET CT.	×						×	×	₉ ×
Chest x-ray	×						×	×	
Bilateral bone marrow Bx, BM cytogenetics. On Follicular lymphoma histology do BM and blood PCR for Bcl-2 rearrangement. On SLL/CLL do ZAP70, CD38 staining and somatic mutation analysis on BM and tumor tissue.	X ₂						X ₂	X_2^2	
Register patient into RevAssist [®] program ¹	×								
Prescribe lenalidomide via RevAssist® 1	×					×			
Rituximab infusion ¹²		*×	×	×	×	*×			
Hematology Test: hematocrit, platelet count, WBC count with differential, Absolute neutrophil count (ANC) and absolute lymphocyte count (ALC). 9, 11	×		×		×	×		×	

Page 8 of 50

Serum chemistry: Blood chemistries should include sodium, potassium, chloride, CO2, blood urea nitrogen (BUN), creatinine, glucose, aspartate aminotransferase (AST), alanine aminotransferase (ALT), total bilirubin, alkaline phosphatase, lactate dehydrogenase (LDH), calcium, phosphorus, and magnesium.	×		×		×	×		×	
Pregnancy test 3,4	*X	×	×	×	×	×		*X	
Tumor lesions assessment	×						×	×	
Response assessment using IWG criteria							×	×	
Record adverse events		×	×	×	×	×		×	
Record concomitant therapies/procedures						×		×	
Obtain Follow-Up anti-cancer treatments									₉ ×
Obtain Follow-Up survival information									₉ ×
Immune Studies 13		×				×			

^{*} Variations of +/- 3 days of the schedule are permitted

¹ Lenalidomide must be prescribed through and in compliance with Celgene's RevAssist® program. Prescriptions must be filled within 7 days.

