Schedule A: Lenalidomide will be administered orally at 20 mg total daily dose on days 1 to 21 of a 28 day cycle in patients with follicular and marginal zone lymphoma. Following cycle 3, if patients fail to show a response (partial or complete) the dose will be increased to 25mg/day. Patients with a diagnosis of small lymphocytic lymphoma (SLL) will begin at a dose of 10 mg total daily on days 1 to 21 of a 28 day cycle. This dose will be escalated by 5mg every 28 days up to 20mg if no toxicity is encountered. If no response is observed by cycle 3, the dose will be increased to 25 mg. (see dose modification for lenalidomide table). A single 375 mg/m2 intravenous dose of rituximab will be given at day 1 of every cycle.

Schedule B: Lenalidomide will be administered orally at 20 mg total daily dose on days 2 to 22 of a 28 day cycle in patients with follicular lymphoma. Following cycle 3, if patients fail to show a response (partial or complete) the dose will be increased to

25mg/day. Patients with a diagnosis of small lymphocytic lymphoma (SLL) will begin at a dose of 10 mg total daily on days 2 to 22 of a 28 day cycle. This dose will be escalated by 5mg every 28 days up to 20mg if no toxicity is encountered. If no response is observed by cycle 3, the dose will be increased to 25 mg. (see dose modification for lenalidomide table). A single 375 mg/m2 intravenous dose of rituximab will be given at day 1, 8,15, and 22 of cycle 1 and on day 1 of every subsequent cycle. In the absence of progression or toxicity, patients will remain on treatment for a total of 12 months. If patients attain a complete response following cycle 6 or 9, lenalidomide will be reduced to 10mg daily for the remaining cycles with the same dosing schedule of rituximab and lenalidomide as described above."

Patients that have documented clinical benefit and no evidence of progression of disease can remain on treatment for a total of 12 months. Treatment will be continued at the cycle 6 dose level with the same dosing schedule of rituximab and lenalidomide as described above.

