Several phase II studies have shown activity with lenalidomide in CLL. Higher doses (25mg) have been associated with increased toxicity in the form of an increased incidence of tumor flare and tumor lysis syndrome (TLS).27,28 Tumor flare has also been correlated with response and may be associated with lenalidomide efficacy. 29 However, lower doses (10mg) appear to be better tolerated and have been associated with fewer cases of tumor flare. Ferrajoli et al treated 35 patients with CLL with a starting dose of 10mg daily for 28 days with a dose escalation to 25mg as tolerated. There were no cases of tumor lysis reported, and only 12% of patients developed tumor flare. The median dose level was 10mg. 30 In another phase II trial with lenalidomide in CLL, 2 out of the first 25 patients experienced TLS at the initial starting dose level (25mg). The study was modified to begin at a lower starting dose and none of the 16 patients who started on the 10mg dose level experienced tumor lysis. The incidence of tumor flare was unchanged, but the severity of reactions decreased significantly.31

Response to therapy will be assessed after 3 cycles and after 6 cycles of chemotherapy. In patients that continue on with extended dosing beyond cycle 6, response will also be evaluated after 9 and 12 cycles of chemotherapy. If after 3 cycles of therapy, there is stable disease without progression, as defined by IWG criteria, the lenalidomide dose will be increased for a total daily dose of 25mg, or 5 mg above the current dose in patients with SLL. If there is evidence of progression of disease, the patient will discontinue study medication.

The rationale for schedule B is derived from studies in both CLL and multiple myeloma suggest a clinical benefit (response rate and PFS) with extended dosing of lenalidomide. In schedule B, the dose of lenalidomide will be reduced in responding patients on cycles 7-12 to minimize potential myelosupression with increased exposure. In addition, significant infusion reactions to rituximab have been noted to occur beyond cycle 2. Although etiology of the infusion reactions is unknown, the severity of the reaction may be potentiated by concurrent dosing of lenalidomide. Ancedotal experience suggests that starting lenalidomide on day 2 of treatment (rituximab on day 1) may lessen the observed toxicity. Dose intensification of rituximab (weekly dosing) will occur in cycle 1 to increase mean serum concentration early in treatment.

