The amount of drug to be administered will be based on BSA. Body surface area will be calculated using a standard nomogram on Cycle 1, Day 1 and at subsequent visits if the subject experiences a >5% change in body weight from the weight used for the most recent BSA calculation.

Schedule A: The planned dose of lenalidomide for patients with follicular lymphoma and marginal zone lymphoma is 20 mg/day, orally on days 1-21 followed by 7 days rest (28 day cycle). Following cycle 3, if patients fail to show a response (partial or complete) the dose will be increased to 25 mg/day.

Schedule B: Lenalidomide will be administered orally at 20 mg total daily dose on days 2 to 22 of a 28 day cycle in patients with follicular lymphoma. Following cycle 3, if patients fail to show a response (partial or complete) the dose will be increased to

25mg/day. Patients with a diagnosis of small lymphocytic lymphoma (SLL) will begin at a dose of 10 mg total daily on days 2 to 22 of a 28 day cycle. This dose will be escalated by 5mg every 28 days up to 20mg if no toxicity is encountered. If no response is observed by cycle 3, the dose will be increased to 25 mg. (see dose modification for lenalidomide table). A single 375 mg/m2 intravenous dose of rituximab will be given at day 1, 8,15, and 22 of cycle 1 and on day 1 of every subsequent cycle. In the absence of progression or toxicity, patients will remain on treatment for a total of 12 months. If patients attain a complete response following cycle 6 or 9, lenalidomide will be reduced to 10mg daily for the remaining cycles with the same dosing schedule of rituximab and lenalidomide as described above.

Dosing will be at approximately the same time each day. The planned dose of lenalidomide for patients with SLL is 10 mg/day, orally on days 1-21 followed by 7 days rest (28 day cycle). If no toxicities are encountered, the dose of lenalidomide in patients with SLL will be increased by 5 mg with each cycle up to 20 mg/day. Following cycle 3, if patients fail to show a response (partial or complete) the dose will be increased to 25 mg/day. Only one cycle of study drug will be supplied to the patient each cycle.(for dose modification guidelines, see Table 2: Dose modification for Lenalidomide) Only one cycle of study drug will be supplied to the patient each cycle.

If a dose of lenalidomide is missed, it should be taken as soon as possible on the same day. If it is missed for the entire day, it should not be made up.

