If these conditions are not met on Day 1 of a new cycle, the subject will be evaluated weekly and a new cycle of lenalidomide will not be initiated until the toxicity has resolved as described above. If lenalidomide dosing was halted during the previous cycle and was restarted with a one-level dose reduction without requiring an interruption for the remainder of the cycle, then that reduced dose level will be initiated on Day 1 of the new cycle. If lenalidomide dosing was omitted for the remainder of the previous cycle or if the new cycle is delayed more than 7 days due to toxicity newly

encountered on the scheduled Day 1, then the new cycle will be started with a one-level dose reduction.

Instructions for dose modifications or interruption during a cycle.

Table 2: Dose Modificatio	n for Lenalidomide	
NCI CTC Toxicity Grade	Day 2-14 of Cycle	≥Day 15 of Cycle
Grade 3 neutropenia associated with fever (temperature ≥ 38.5° C) or Grade 4 neutropenia	 Hold (interrupt dose). Follow CBC weekly. If neutropenia has resolved to ≤ grade 2 restart at next lower dose level and continue the cycle until Day 21. 	Omit lenalidomide for remainder of cycle If neutropenia is the only toxicity for which a dose reduction is required. G-CSF may be used and the dose maintained for the next cycle at the investigators discretion.
Thrombocytopenia [†] ≥Grade 3 (platelet count < 50,000/mm³)	 Hold (interrupt dose). Follow CBC weekly. If thrombocytopenia resolves to ≤ grade 2 restart at next lower dose level and continue the cycle until Day 21. 	Omit lenalidomide for remainder of cycle
Non-blistering rash Grade 3	 If Grade 3 hold (interrupt) dose. Follow weekly. If the toxicity resolves to ≤ grade 1 prior to Day 21 restart at next lower dose level and continue the cycle until Day 21. 	Omit lenalidomide for remainder of cycle.
Grade 4	 Discontinue lenalidomide study drug. 	 Discontinue lenalidomide study drug.
Desquamating (blistering) rash- any Grade	 Discontinue lenalidomide study drug. 	Discontinue lenalidomide study drug.
Erythema multiforme ≥ Grade 3	 Discontinue lenalidomide study drug. 	Discontinue lenalidomide study drug.
Sinus bradycardia/ other cardiac arrhythmia Grade 2	 Hold (interrupt) dose. Follow at least weekly. If the toxicity resolves to ≤ grade 1 prior to Day 21 restart at next lower dose level and continue the cycle until Day 21. 	Omit lenalidomide for the remainder of the cycle.
≥ Grade 3	Discontinue lenalidomide study drug.	 Discontinue lenalidomide study drug.

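### Drug Administration puts the 15 Schedule B SLL patients under two lenalidomide calendars, days 2-22 and, in a paragraph with no schedule label, days 1-21

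*Combined protocol and SAP*

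**What the plan says.** Section 5, Drug Administration, has three consecutive pieces of lenalidomide text.

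- The Schedule A paragraph names two histologies and not SLL: "Schedule A: The planned dose of lenalidomide for patients with follicular lymphoma and marginal zone lymphoma is 20 mg/day, orally on days 1-21".
- The Schedule B paragraph covers follicular lymphoma and SLL. SLL patients "will begin at a dose of 10 mg total daily on days 2 to 22 of a 28 day cycle".
- A further paragraph has no schedule label. It opens with a general remark on the time of day for dosing, and then says: "The planned dose of lenalidomide for patients with SLL is 10 mg/day, orally on days 1-21 followed by 7 days rest".

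Elsewhere the calendars are kept apart. Overall design has, under Schedule A, "Patients with a diagnosis of small lymphocytic lymphoma (SLL) will begin at a dose of 10 mg total daily on days 1 to 21", and under Schedule B the days 2-22 wording. The synopsis gives, for Schedule B, "Lenalidomide 10 mg po daily, with escalation up to 25 mg on days 2-22 of 28 day cycle for patients with small lymphocytic lymphoma".

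The Schedule B rationale in Section 5 says that anecdotal experience suggests "starting lenalidomide on day 2 of treatment (rituximab on day 1) may lessen the observed toxicity".

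Two instructions on dose changes do not distinguish the schedules. In the Dose Modification table, patients whose toxicity resolves are to "restart at next lower dose level and continue the cycle until Day 21". If a dose was halted and restarted one level lower during a cycle, "then that reduced dose level will be initiated on Day 1 of the new cycle". Two tables in Section 5 are numbered 2. The one meant here is Dose Modification for Lenalidomide, not the SLL dose steps.

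**The concern.** A Schedule B SLL patient meets the description in both the labelled Schedule B paragraph and the unlabelled one, and the two give different dosing days. Nothing in Drug Administration limits the unlabelled sentence to Schedule A. It comes after the Schedule B text and sits among remarks that apply to everyone, so it can be read as a general rule for SLL.

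The day 2 start is one of the features that distinguish Schedule B. If some of these patients start on day 1 and others on day 2, their toxicity data describe a mixture of calendars. Section 10 says the cohorts are meant to help characterise differences in response and toxicity between subgroups, and the monitored toxicity is assessed at the end of cycle 1. An uncertain calendar weakens what can be said about Schedule B in SLL.

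**Working it through.** The point rests on the text, so the statements are set side by side. The only arithmetic is a count of days and patients.

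**SLL calendars by place**

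| Place | Schedule A SLL | Schedule B SLL | No label |
|---|---|---|---|
| Synopsis | days 1-21 | days 2-22 | none |
| Overall design | days 1-21 | days 2-22 | none |
| Drug Administration | not stated | days 2-22 | days 1-21 |

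The empty Schedule A entry in the last row is the best clue to the origin of the unlabelled sentence. It supplies exactly the text that is missing, and it matches the Schedule A wording for SLL in Overall design.

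**Dosing days per cycle**

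- Days 1-21: 21 - 1 + 1 = 21 days.
- Days 2-22: 22 - 2 + 1 = 21 days.

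Both agree with the 21 days in every 28 of the dose-step tables, so those tables cannot settle which calendar is meant. The calendars differ only at the ends: one includes day 1 and not day 22, the other the reverse.

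**Effect of the Day 21 wording**

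- A Schedule B cycle that ends at Day 21 spans days 2-21: 21 - 2 + 1 = 20 days, before any held days are removed.
- The difference is one day, 1/21 = 4.8% of the planned dosing days in that cycle.
- The wording stands in six toxicity rows: neutropenia, thrombocytopenia, grade 3 non-blistering rash, grade 2 arrhythmia, grade 2-3 allergic reaction, and other lenalidomide-related non-hematologic toxicity. In each row it applies to events on days 2-14.

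**Patients reached** (enrolment split from Overall design)

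- Unlabelled SLL sentence: 15 Schedule B SLL patients. 15/155 = 9.7% of the trial; 15/45 = 33% of Schedule B.
- Day 21 and Day 1 wording: at most 15 SLL + 30 follicular = 45 patients, 45/155 = 29.0% of the trial, and only those whose dose is interrupted or reduced.
- Monitored toxicity window, cycle 1: 15 patients x 1 day 1 infusion = at most 15 infusions.

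**Link to the monitoring rules**

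Section 10 gives cohort 3 a single toxicity boundary for all 45 SLL patients and does not divide it by schedule. The only Schedule B cohort with its own boundary is cohort 4, follicular lymphoma, which the SLL sentence does not touch. No prior, boundary or operating characteristic depends on the dosing calendar.

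**The case against.** The strongest reply is that this is a missing label and nothing more. The synopsis, Overall design and the labelled paragraph immediately above all give days 2-22 for SLL on Schedule B. The trial is run at one institution, so a misreading is less likely than it would be across many sites. This largely stands, and it makes the error local. It does not remove it, because Drug Administration is an operative dosing section and contradicts itself for a defined group of patients.

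Four stronger readings are tempting, and the documents do not support them.

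- *Schedule B patients in general could be moved to the Schedule A calendar.* The unlabelled sentence concerns SLL only, so the 30 Schedule B follicular patients are outside it. The Day 21 wording costs at most one dose in an already interrupted cycle and cannot cause a day 1 start. The Day 1 wording on reduced doses bears on the start day, but only after a mid-cycle reduction.
- *Day 1 dosing exposes patients to an interaction that Schedule B was built to avoid.* The rationale leads with extended lenalidomide dosing, calls the cause of the infusion reactions unknown, and rests the day 2 start on anecdote. Schedule B also gives rituximab on days 8, 15 and 22 of cycle 1, all within lenalidomide days 2-22, so same-day dosing is already part of it.
- *Up to 180 infusions are affected.* That is 15 patients x 12 cycles. It requires every patient to complete 12 cycles and to be given the other calendar each time, and nothing suggests this. Only cycle 1 enters the toxicity monitoring. The rationale reports the infusion reactions as occurring beyond cycle 2, which loosens the link to that window further.
- *A formal comparison of schedules is compromised.* The Analysis Plan names no test of Schedule A against Schedule B.

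**Conclusion.** The contradiction is real and sits in live dosing instructions: 15 Schedule B SLL patients are covered by two different calendars in the same section. The likeliest explanation is Schedule A text that lost its label. That is an inference from the gap in the Schedule A paragraph and the match with Overall design; the documents do not say so.

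The consequence is modest. Mixed calendars would blur one intended feature of Schedule B and the cycle 1 toxicity data of those patients, with at most 15 day 1 infusions in the monitored cycle. This ceiling assumes full planned enrolment and that all 15 follow the unlabelled paragraph; the number who would do so cannot be known from the documents. The Day 21 and Day 1 wording is a lesser inconsistency of the same kind, with a reach of at most 45 patients. The sample size and the stopping boundaries are unaffected.

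**What to change.** The sponsor should reconcile Overall design, Drug Administration, the instructions for starting a new cycle and the Dose Modification table, in two steps.

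1. State which schedule the unlabelled SLL paragraph applies to. It should not simply be deleted: if it is Schedule A text, it is the only SLL dosing instruction for that schedule in Drug Administration, and 30 patients depend on it.
2. Make the Day 21 wording in the table and the Day 1 wording for reduced doses consistent with each schedule as the sponsor intends it.

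Which calendar is right is for the sponsor and investigators to decide. Giving the two tables now numbered 2 different numbers would make the cross-references clear. The cost is a label and a few words in the next amendment. If Schedule B SLL patients have already been treated, the day lenalidomide was started in each cycle can be taken from their dosing diaries and reported with the toxicity data.

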Patients who take more than the prescribed dose of lenalidomide should be instructed to seek emergency medical care if needed and contact study staff immediately.

Subjects experiencing adverse events may need study treatment modifications. See Table 2.

Special Handling Instructions

Women of childbearing potential should not handle or administer the clinical dosage forms unless they are wearing gloves.

Dose Continuation, Modification and Interruption

Subjects will be evaluated for AEs at each visit with the NCI CTCAE v3.0, see below for full instruction on initiation of a new cycle of therapy and dose modifications during a cycle of therapy.

Lenalidomide Dose Adjustment Steps

Table 1 outlines lenalidomide dose adjustment steps

Table 1: LENALIDOMIDE Dos	se Adjustment Steps	
	20 mg daily for 21 days every 28 days	
Starting Dose		
Dose Level +1	25 mg daily for 21 days every 28 days	
Dose Level –1	15 mg daily for 21 days every 28 days	
Dose Level –2	10 mg daily for 21 days every 28 days	
Dose Level –3	5 mg daily for 21 days every 28 days	

Table 2: LENALIDOMIDE Dos	e Adjustment Steps in SLL
Starting Dose	10 mg daily for 21 days every 28 days
Dose level +1	15 mg daily for 21 days every 28 days
Dose level +2	20 mg daily for 21 days every 28 days
Dose level +3	25 mg daily for 21 days every 28 days
Dose level -1	5 mg daily for 21 days every 28 days
Dose level -2	5 mg daily for 14 days every 28 days
Dose level -3	Hold therapy

Instruction for initiation of a New Cycle

A new course of treatment may begin on the scheduled Day 1 of a new cycle if:

- The ANC is $\geq 1,000/\mu L$;
- The platelet count is $\geq 50,000/\mu L$;
- Any lenalidomide-related allergic reaction/hypersensitivity or sinus bradycardia/ other cardiac arrhythmia adverse event that may have occurred has resolved to ≤ grade 1 severity;
- Any other lenalidomide-related adverse event that may have occurred has resolved to ≤ grade 2 severity.

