Allergic reaction or hypersensitivity Grade 2-3	 Hold (interrupt) dose. Follow at least weekly. If the toxicity resolves to ≤ grade 1 prior to Day 21 restart at next lower dose level and continue the cycle until Day 21. 	Omit lenalidomide for the remainder of the cycle.
Grade 4	Discontinue lenalidomide study drug.	Discontinue lenalidomide study drug

Table 2: Dose Modification	n for Lenalidomide	
NCI CTC Toxicity Grade	Day 2-14 of Cycle	≥Day 15 of Cycle
Venous thrombosis/embolism ≥ Grade 3	 Hold (interrupt) dose and start anticoagulation; restart at investigator's discretion (maintain dose level). 	Omit lenalidomide for remainder of cycle. Anticoagulation measures as described in Conncomitant therapy section below.
other non-hematologic toxicity assessed as Lenalidomide-related ≥ Grade 3	 Hold (interrupt) dose. Follow at least weekly. If the toxicity resolves to ≤ grade 2 prior to Day 21 restart at next lower dose level and continue the cycle until Day 21. 	Omit lenalidomide for remainder of cycle.
Hyperthyroidism or hypothyroidism	Omit lenalidomide for remainder of cycle, evaluate etiology, and initiate appropriate therapy. Restart lenalidomide next cycle (decrease dose by one dose level).	Omit lenalidomide for remainder of cycle, evaluate etiology, and initiate appropriate therapy. Restart lenalidomide next cycle (decrease dose by one dose level).

[†] If patient had low baseline platelets due to prior to study entry, dose reduction not required.

Dose Escalation

In schedule B, all patients in a complete response will reduce lenalidomide to 10mg daily on cycles 7-12.

If after 3 cycles of therapy, there is stable disease without evidence of progression as defined by IWG criteria, the lenalidomide dose will be increased to 25 mg per day (dose level +1) or 5 mg above the current dose in patients with SLL. The initiation of the next cycle will only be initiated if there is no evidence of toxicity as outlined above in the Instructions for Initiation of a New Cycle.

Treatment compliance

Subjects will be asked to maintain a diary to record the drug administration.

Prohibited concomitant therapy

Concomitant use of sargramostim (GM-CSF), other anti-cancer therapies, including radiation, thalidomide, or other investigational agents is not permitted while subjects are receiving study drug during the treatment phase of the study.

Discontinuation of Study Treatment

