The trial consists of 4 parallel patient cohorts. Using dose schedule A we will enroll 50 patients with follicular lymphoma (cohort 1) and 30 patients with marginal zone lymphoma (cohort 2). We will enroll 45 patients with small lymphocytic lymphoma (cohort 3). We will also enroll 30 patients with follicular lymphoma patients and treat them with dosing schedule B (cohort 4). This will allow the investigators to better characterize and define possible differences in the response rate and toxicity profiles for each of the study subgroups.

The overall response, denoted as OR (to be assessed at the end of 3 cycles), and toxicity (to be assessed at the end of the first cycle) will be monitored simultaneously for each of the subgroups separately using the Bayesian approach of Thall, Simon, Estey (1995, 1996) as extended by Thall and Sung (1998). Toxicity is defined as any grade 3 or 4 nonhematologic toxicity.

Cohort 1: For the subgroup of patients with follicular lymphoma and treated with dosing schedule A, historical data on similar patients show an overall response rate of 70% and toxicity rate of 20%. However, the information was down-weighted to reflect the same marginal OR and toxicity rates in 10 patients. Independence was assumed between OR and toxicity. It is expected for the current trial that the two-drug combination will improve the OR rate to 80% while the toxicity rate is maintained at 30%. A sample size of 50 patients ensures that, if the trial is not terminated early, a posterior 90% credibility interval for overall response rate will have width of 0.19 at most, under the assumption of an 80% of overall response rate. The probabilities of OR and toxicity for the historical data are modeled by beta distributions (Beta(7, 3) and Beta(2, 8), respectively). The prior probabilities of OR and toxicity for the experimental regimen are also modeled by beta distributions

(Beta(1.4, 0.6)) and Beta(0.4, 1.6), respectively), which have the same *means* as the corresponding beta distributions for the historical data. Denoting the historical probabilities of overall response rate and toxicity rate by {p(OR,H), p(TOX,H)}, the following decision criteria will be applied:

- 1) Let E correspond to the experimental treatment, stop if $Prob\{p(OR,H) + \delta_{OR} > p(OR,E) \mid data\} > 0.90$, where $\delta_{OR} = 0.1$
- 2) Stop if Prob{p(TOX,H) + δ_{TOX} < p(TOX,E)| data}>0.90, where δ_{TOX} =0.1

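### Two rules give different cycle 4 lenalidomide doses to SLL patients who have stable disease after cycle 3 and are below 20 mg

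*Combined protocol and SAP*

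**What the plan says.** All the dosing text is in Section 5.

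- **SLL ladder.** SLL patients start at 10 mg. Overall design then says: "This dose will be escalated by 5mg every 28 days up to 20mg if no toxicity is encountered".
- **Rule 1, a fixed target.** Overall design, in the SLL text for both schedules: "If no response is observed by cycle 3, the dose will be increased to 25 mg". Drug Administration repeats it for SLL: "Following cycle 3, if patients fail to show a response (partial or complete) the dose will be increased to 25 mg/day". Neither sentence depends on the current dose.
- **Rule 2, a step.** For stable disease after three cycles, the response-assessment paragraph of Overall design and the Dose Escalation paragraph both give 25 mg, "or 5 mg above the current dose in patients with SLL".
- **Progression.** Overall design stops study drug in patients who progress.
- **SLL dose levels.** The SLL table under Lenalidomide Dose Adjustment Steps runs from 10 mg (start) through 15, 20 and 25 mg (levels +1 to +3). Downward, level -1 is 5 mg for 21 days and level -2 is "5 mg daily for 14 days every 28 days".
- **Reductions.** Under Instruction for initiation of a New Cycle, if dosing was interrupted in the previous cycle and resumed one level lower, "then that reduced dose level will be initiated on Day 1 of the new cycle". A one-level reduction also applies if the rest of the previous cycle was omitted or the new cycle is delayed by more than 7 days for toxicity.

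**The concern.** Stable disease is a failure to reach a partial or complete response, so a stable-disease SLL patient satisfies both rules. Each rule appears in two places, so this is not a single slip of the pen, and no order of precedence is given.

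The patients for whom the answers differ exist by design. The ladder rises only in the absence of toxicity, with no grade stated, so a patient can be held at 10 or 15 mg without any dose interruption. Under Rule 1 the larger jump goes mainly to patients who have already had toxicity. Overall design reports that 25 mg in CLL was associated with more tumor flare and tumor lysis, and gives this as the context for the low SLL start.

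The formal stopping rule is no backstop at that point. Section 10, Statistical Methodology, monitors "toxicity (to be assessed at the end of the first cycle"), so events in cycle 4 do not enter the boundary.

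**Working it through.** The plan gives no figure to reproduce, so the two rules are compared at each possible current dose.

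**Inputs.** Rule 1: 25 mg. Rule 2: current dose + 5 mg. Course length: 21 days. Levels: SLL table, with 25 mg as level +3.

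| Current dose (level) | Rule 1 | Rule 2 | Gap per day | 21-day totals | Ratio | Levels climbed under Rule 1 |
|---|---|---|---|---|---|---|
| 20 mg (+2) | 25 | 20 + 5 = 25 | 0 | 525 vs 525 mg | 1.00 | 1 |
| 15 mg (+1) | 25 | 15 + 5 = 20 | 5 mg | 525 vs 420 mg | 1.25 | 2 |
| 10 mg (start) | 25 | 10 + 5 = 15 | 10 mg | 525 vs 315 mg | 1.67 | 3 |
| 5 mg (-1) | 25 | 5 + 5 = 10 | 15 mg | 525 vs 210 mg | 2.50 | 4 |

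**Who reaches each row.** A patient who takes every step is on 10, 15 and 20 mg in cycles 1 to 3, and the rules agree. A patient held once is at 15 mg, and one held twice at 10 mg. A patient reaches 5 mg only by a toxicity reduction from 10 mg. If that reduction came in cycle 3, the new-cycle rules set the cycle 4 dose. The 5 mg row therefore needs a reduction in cycle 1 or 2 followed by an uneventful cycle 3 at 5 mg.

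**Do other provisions choose between the rules?**

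- The new-cycle criteria decide whether a cycle may start, not at what dose. They accept a neutrophil count of 1,000/µL, platelets of 50,000/µL and most lenalidomide-related events at grade 2. A patient held at 10 mg can meet them.
- The reduction rules look only at the immediately preceding cycle or a delayed start. They do not cover a patient held or reduced earlier who was stable through cycle 3.
- The dose tables list levels and toxicity actions. None selects the dose for escalation after cycle 3.

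**How many patients?** The documents allow only a ceiling. With 45 SLL patients, all non-responders number 45 × (1 − 0.60) = 18 at the planned response rate, or 45 × (1 − 0.50) = 22.5 at the historical rate. Both counts still include progressors, non-responders already at 20 mg, and patients whose dose is set by the reduction rules. The true number is smaller and cannot be derived.

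Doses below 20 mg may not be rare. Overall design describes a CLL study that started at 10 mg and escalated to 25 mg as tolerated, and reports: "The median dose level was 10mg". Its population and its daily 28-day schedule differ from this trial's, so it is indicative only.

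**The case against.** The best counter-argument is that only one reading was intended. The 25 mg sentence directly follows the ladder, and for a patient on schedule 25 mg is simply the rung above 20 mg. On that view the figure is shorthand for one step up. The ladder sentence has no end date at cycle 3, so below 20 mg its own step would still be 5 mg. The dedicated Dose Escalation paragraph states the SLL exception. This is plausible and may well be what the authors meant. The text does not say so, however, and two physicians could each follow the protocol and give different doses.

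Other objections stand in part:

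- **Harm.** The lysis cases quoted in Overall design occurred at a 25 mg starting dose: 2 of the first 25 patients in one study. The study that started at 10 mg and escalated reported no lysis and 12% flare. The documents contain no data on a multi-level jump in cycle 4, so its risk is unquantified in either direction.
- **Safeguards.** Holds, reductions and investigator discontinuation still apply in cycle 4, and adverse events are still recorded every cycle.
- **Monitoring.** Toxicity monitoring is confined to cycle 1 in every cohort, whichever dose rule applies. The conflict does not alter that boundary; the boundary just does not cover this period.
- **Largest figures.** The 2.5-fold and four-level figures belong to the narrow 5 mg case.

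**Conclusion.** The inconsistency is real and should be fixed. For an SLL patient with stable disease after cycle 3 and a current dose of 15, 10 or 5 mg, the protocol gives two doses that differ by 5, 10 or 15 mg/day, with no rule of precedence.

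This rests on reading the 25 mg sentences literally, because no limit to patients at 20 mg is stated. Responders, progressors, patients at 20 mg and patients whose cycle 4 dose is set by a toxicity reduction are not affected. Response for monitoring is assessed at the end of cycle 3, before the disputed dose, so the response boundary is also unaffected. The consequence is inconsistent, and possibly unintended, exposure in patients who mostly have had earlier toxicity. No error rate or operating characteristic changes.

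**What to change.** In the SLL text of Overall design (both schedules) and Drug Administration, replace the fixed 25 mg target with the rule the protocol already states twice: one level (5 mg) above the current dose on the SLL table, to a maximum of 25 mg.

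Two additions are needed:

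- The toxicity reductions under Instruction for initiation of a New Cycle take precedence over this escalation.
- From SLL level -2 the next level is 5 mg for 21 days. This is new wording: that level differs from the one above it in days rather than daily dose, so adding 5 mg does not lead to a level on the table.

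The cost is a wording amendment and a clarification to the treating team. Sample size, boundaries and assessments stay as they are. The trade-off is that some stable-disease SLL patients reach 25 mg later or not at all. If the sponsor does intend a direct move to 25 mg from any dose, it should say so, justify it, and remove the 5 mg rule.
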